5.5.2 Documentation of Prior and Concomitant Medication Use

All concomitant medications and concurrent therapies will be documented. Dose, route, unit frequency of administration, indication for administration, and dates of medication administration will also be captured in source documents and on the appropriate CRF.

5.6 Rescue therapy

If poor blood pressure control persists (SBP≥160mmHg or DPB≥100 mmHg) after adjusting spironolactone or finerenone to the maximum dose for 2 to 4 weeks, amlodipine can be treated remedial (5 to 10mg/day)

5.7 Treatment for Hypokalemia

For patients with low potassium (serum potassium <3.5mmol), potassium supplementation will be given according to the severity of hypokalemia before randomization, and potassium supplementation is stopped 2 weeks after starting MRA treatment, and then the treatment plan is adjusted according to the blood potassium reexamination in V4 (4 weeks after starting MRA treatment): If the serum potassium is <3.5mmol/1, MRA should be supplemented with 20mg qd up to the maximum dose, and the serum potassium should be re-checked 4 weeks later (V5), and the treatment

regimen should be adjusted according to the above principles.

6 Study Procedures

6.1 Informed Consent

Written consent will be obtained from all patients before any protocol-specific procedures are performed.

Information about the study will be given to the patient both verbally and in writing. The written patient information will explain the objectives of the study, potential risks and benefits, and the impact of early withdrawal on the scientific validity of the study. The patient must have adequate time to read the information and to ask the Investigator any questions. The Investigator must ensure that the patient has understood the information provided before written consent is obtained. If there is any doubt as to whether the patient has understood the written or verbal information, the patient must not enter the study.

6.2 Screening Period (Visit 1, Week -2 ~0)

For the screening test and the confirmatory tests, antihypertensive medication is withheld or changed according to the guideline.

The following procedures will be performed at Visit 1:

- Obtain informed consent:
- Assess eligibility based on Inclusion/Exclusion Criteria;
- Perform 24-hour ABPM;
- Record demographics and medical/surgical history;
- Assess and record AEs;
- Record prior medications;
- Measure weight and height;
- Record vital signs;
- Measure seated BP and heart rate;
- ECG;
- •Collect urine sample for urinalysis and blood samples for FPG, ALT, AST, creatinine, electrolyte, PAC and PRC, UACR

6.3 Treatment Period

6.3.1 Baseline and Randomization (Visit 2, Day 0)

The following procedures will be performed at Visit 2:

- Check inclusion and exclusion criteria;
- Randomization to finerenone or spironolactone once daily;
- Record pre-dose office seated BP;
- Dispense the study drug;
- Record concomitant medications;
- Record adverse events;
- First administration of study drug;
- Perform the following routine safety evaluations pre-dose;
- Record weight;
- Record vital signs;
- Perform physical examination (general appearance, skin, heart, lungs, and abdomen);

6.3.2 Telephone Call (Visit 3 and Visit 5, Week 2 and Week 10 respectively)

The following procedures will be performed at Visit 3 and Visit 5:

- Assess and record AEs;
- Record concomitant medications;
- Perform adherence counselling;
- Record home seated BP;
- Provide the following instructions for the next visit.

Patients should take their scheduled morning doses of background antihypertensive medications at home on the morning of their next visit; Patients must bring their background antihypertensive medications to the clinical site for their next visit; and Patients should not exercise, smoke, or consume caffeinated beverages or food for at least 2 hours prior to the next visit.

6.3.3 Visit 4, Week 4.

The dose used in the assigned regimen will be doubled after 4 weeks if, at that time, the patient remains a mean office seated BP of 140 mm Hg or higher (systolic) or 90 mm Hg or higher (diastolic): at week 4, the dose will be doubled from 20 mg once daily to 40 mg once daily (maximum dose) in both finerenone and spironolactone group.

The following procedures will be performed at Visit 4:

- Assess and record AEs:
- Record concomitant medications;
- Record office seated BP;
- Assess treatment adherence based on pill counts;
- Perform the following routine safety evaluations pre-dose;
- · Record weight;

- Record vital signs;
- Perform physical examination (general appearance, skin, heart, lungs, and abdomen);
- Measure standing BP and heart rate
- Collect blood samples for the following:

Serum potassium

Serum creatinine

6.3.4 Visit 5, Week 8.

Same to the Visit 4

6.3.5 End of Treatment (Visit 7, Week 12)

The following procedures will be performed at Visit 6:

- Perform 24-hour ABPM
- Assess and record AEs:
- Record concomitant medications;
- Assess treatment adherence based on pill counts;
- Perform the following routine safety evaluations pre-dose;
- · Record weight;
- Record vital signs;
- Perform physical examination (general appearance, skin, heart, lungs, and abdomen);

Measure standing BP and heart rate

- Collect urine sample for urinalysis; and
- Collect blood samples for the following:

PAC

PRC

Serum potassium

Serum creatinine

UACR

Study visits will follow the Schedule of Procedures (Appendix A).

7 Efficacy Assessments

7.1 Primary Efficacy Endpoint

The change from baseline in 24-hour systolic blood pressure (SBP) assessed by 24-hour ABPM compared to spironolactone after 12 weeks of finerenone therapy in patients with PA

7.2 Secondary Efficacy Endpoints

- Change from baseline in 24-hour diastolic blood pressure (DBP) assessed by 24-hour ABPM;
- Blood pressure control rate at the end of the study;

Note: Blood pressure control rate is defined as the percentage of patients with mean seated office BP<140/90 mmHg.

- Change from baseline in daytime SBP assessed by 24-hour ABPM;
- Change from baseline in daytime DBP assessed by 24-hour ABPM;
- Change from baseline in nighttime SBP assessed by 24-hour ABPM;
- Change from baseline in nighttime DBP assessed by 24-hour ABPM;
- Change from baseline in office SBP;
- Change from baseline in office DBP;
- Change from baseline in serum potassium;
- Hypokalemia control rate at the end of the study

Note: Hypokalemia control rate is defined as the percentage of hypokalemic patients with serum potassium>3.5mmol/l at the end of the study.

• Change from baseline in plasma renin.

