2.2 The secondary efficacy endpoints

The secondary efficacy endpoints include the followings:

- Change from baseline in 24-hour diastolic blood pressure (DBP) assessed by 24-hour ABPM;
- Blood pressure control rate at the end of the study;

Note: Blood pressure control rate is defined as the percentage of patients with mean seated office BP < 140/90 mmHg.

- Change from baseline in daytime SBP assessed by 24-hour ABPM;
- Change from baseline in daytime DBP assessed by 24-hour ABPM;
- Change from baseline in nighttime SBP assessed by 24-hour ABPM;
- Change from baseline in nighttime DBP assessed by 24-hour ABPM;
- Change from baseline in office SBP;
- Change from baseline in office DBP;
- Change from baseline in serum potassium;
- Hypokalemia control rate at the end of the study

Note: Hypokalemia control rate is defined as the percentage of hypokalemic patients with serum potassium>3.5mmol/l at the end of the study.

• Change from baseline in plasma renin

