5.2 Randomization and Treatment Period

Patients who meet all eligible criteria will be randomized 1:1 into 1 of the 2 treatment groups (finerenone and spironolactone). The dose used in the assigned regimen will be doubled after 4 weeks if, at that time, the patient remains a mean office seated BP of 140 mm Hg or higher (systolic) or 90 mm Hg or higher (diastolic): at week 4, the dose will be doubled from 20 mg once daily to 40 mg once daily (maximum dose) in both finerenone and spironolactone group. The dose will not be increased if the patient has severe TAEs. In these instances, the dose is either maintained or decreased, as determined by the investigator.

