10.1 Analysis Populations

The following analysis populations are defined for the different types of data analysis:

• Intention-to-treat (ITT) Population

The ITT Population will include all patients randomized into the study. Treatment classification will be based on the randomized treatment;

• Modified intention-to-treat (mITT) Population

The mITT Population will include patients randomized and received at least 1 dose of any study drug. Treatment classification will be based on the randomized treatment. The mITT population will be used for the primary analysis of all efficacy endpoints;

• Per Protocol (PP) Population

The PP Population will include all patients in the mITT population and who did not experience a major protocol deviation that potentially impacted the primary efficacy endpoint. The PP population, along with the reason for exclusion, will be finalized prior to study end.

Safety Population

The Safety Population will include all patients who receive at least 1 dose of any randomized study drug. Treatment classification will be based on the actual treatment received. The Safety Population will be the primary population used for the safety analyses.

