10.2 Efficacy analysis

The primary efficacy analysis will compare the change in 24-hour SBP assessed by ABPM from baseline (Visit 2) to the End of Treatment (Visit 7) between finerenone and spironolactone. Statistical analyses will be primarily descriptive. No formal hypothesis testing will be conducted. Descriptive statistics (eg, mean, standard deviation, median, minimum and maximum) will be presented for continuous variables. Frequencies and percentages will be presented for categorical and ordinal variables.

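### As written, the blood pressure control rate counts a patient brought below 140/90 on rescue amlodipine as controlled, so unequal rescue use would favour the arm with more rescue

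*Protocol*

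**What the plan says.** The endpoint is the "Blood pressure control rate at the end of the study". Its note in section 7.2 reads "Blood pressure control rate is defined as the percentage of patients with mean seated office BP<140/90 mmHg", and Synopsis 2.2 says the same: "Blood pressure control rate is defined as the percentage of patients with mean seated office BP < 140/90 mmHg". Neither place mentions rescue.

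Section 5.6 sets the rescue condition: "If poor blood pressure control persists (SBP≥160mmHg or DPB≥100 mmHg) after adjusting spironolactone or finerenone to the maximum dose for 2 to 4 weeks", then "amlodipine can be treated remedial (5 to 10mg/day". It applies to both arms and is permissive. Section 5.2 sets the time of the step-up: "at week 4, the dose will be doubled from 20 mg once daily to 40 mg once daily (maximum dose". Section 10.1 fixes the analysis set: "The mITT population will be used for the primary analysis of all efficacy endpoints". That set is everyone randomized who took at least one dose, so rescue does not remove a patient from it.

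Two other places bear on the point. Section 5.5.1 lists any antihypertensive beyond the screening background treatment as excluded and makes no exception for rescue. Section 4.3 item 3 withdraws a patient who took an excluded drug for more than one week and is still on it two weeks before the last visit. Section 4.3 also asks sites to attempt the Visit 7 assessments in withdrawn patients.

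**The concern.** A responder rule settles who counts as a success of the assigned drug, and this one is complete as it stands. A patient who stays at or above 160 systolic or 100 diastolic on the maximum study dose has not been controlled by that drug. If amlodipine then brings the reading below 140/90, the rule records a success for finerenone or spironolactone.

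Rescue is triggered by poor control, so it may be used more in the arm whose drug works less well. The control rate would then understate the difference between the drugs, or even reverse it. Section 10.4 frames the trial as a non-inferiority comparison, so readers will use a similar control rate as support for that claim. The primary endpoint has a related exposure: "The primary efficacy analysis will compare the change in 24-hour SBP assessed by ABPM", and a Week 12 recording made on amlodipine contains amlodipine's effect.

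**Working it through.** **The plan's own figure.** Section 10.4 uses SDs of 12.5 and 9.5 mmHg, a margin of 4 mmHg, one-sided α = 0.025 and 80% power.
- Common SD = √((12.5² + 9.5²)/2) = 11.10.
- The normal approximation gives 121 per arm (242 in total). The t-based calculation gives 122 per arm, or 244, with power 0.800.
- 122/0.8 = 152.5, rounded up to 153 per arm, or 306.

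The stated 244 and 306 reproduce and are not in dispute. No expected rate, margin or power is given for the control rate.

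**Can rescue act before Week 12?** Yes. With a step-up at Week 4, the 2 to 4 weeks at maximum dose end at Weeks 6 to 8. Appendix A schedules the next office reading at Week 8, so the ordinary case is about 12 − 8 = 4 weeks on amlodipine. An earlier start would need an unscheduled visit. If the step-up comes at Week 8, which section 5.1 permits by adjusting every 4 weeks, the condition is reached only at Weeks 10 to 12.

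**Effect on the endpoint.** For each arm let p be the share controlled without rescue, r the share rescued, and c the share of rescued patients below 140/90 at Week 12. The written rule reports p + r·c. Counting rescued patients as not controlled reports p. The two versions of the between-arm difference differ by

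r1·c1 − r0·c0, which equals c × (r1 − r0) when c is the same in both arms.

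**Size.** The documents give neither r nor c. The values below are assumptions, with arm 1 the arm with more rescue.

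| Rescue, arm 1 vs arm 0 | c = 0.1 | c = 0.3 | c = 0.5 |
|---|---|---|---|
| 5% vs 5% | 0 | 0 | 0 |
| 10% vs 5% | 0.5 points | 1.5 points | 2.5 points |
| 20% vs 5% | 1.5 points | 4.5 points | 7.5 points |

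Example: control without rescue 45% vs 50% (difference −5.0 points), rescue 20% vs 5%.
- c = 0.3: (45 + 6.0) − (50 + 1.5) = −0.5 points.
- c = 0.5: (45 + 10.0) − (50 + 2.5) = +2.5 points.

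**Against sampling error.** At a 50% control rate the standard error of the difference is √(2 × 0.25/153) = 5.7 points with 153 per arm and √(2 × 0.25/122) = 6.4 points with 122. Most of the table lies below one standard error.

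**How large can c be?** A rescued patient counts as controlled only after a fall of more than 160 − 140 = 20 mmHg if systolic pressure was the trigger, or more than 100 − 90 = 10 mmHg if diastolic was. The upper end, c = 0.5, is therefore demanding for systolic-triggered patients.

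**The case against.** **Control regardless of rescue is a legitimate measure.** It describes a treatment policy, and the handling of data after rescue is often left to a statistical analysis plan, which is not at hand. This stands for the primary endpoint: the protocol states nothing wrong there, and a sensitivity analysis is an addition. It is weaker for the control rate, because the protocol itself gives the full responder rule twice without saying that rescue is meant to count.

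**The exclusion and withdrawal rules might remove rescued patients.** Read strictly, sections 5.5.1 and 4.3 item 3 make a patient on amlodipine near Week 12 a withdrawal. That does not close the gap, since the Visit 7 assessments are still requested and the analysis set keeps the patient. It does show that the three sections cannot all be followed.

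**Scoring rescue as failure has its own weakness.** Rescue is optional, no blinding is described, and under section 5.3 the investigator dispenses by assigned group. The decision to rescue could itself influence the result. This stands and is the reason to show both versions.

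**A stronger reading is tempting.** A reader might infer that the plan materially raises the risk of a false non-inferiority finding. Suppose rescue is 10 points more frequent in one arm and lowers 24-hour systolic pressure by 8 to 10 mmHg per rescued patient. That hides 0.8 to 1.0 mmHg. With SE = √((12.5² + 9.5²)/122) = 1.42 mmHg, the false non-inferiority probability at a true 4 mmHg deficit goes from 2.5% to about 8% to 10%. The arithmetic is right, but the documents support neither the imbalance nor the effect size. The pilot in section 1.1 reports nearly identical falls in office systolic pressure (−17.7 and −17.1 mmHg) and a numerically larger 24-hour fall on finerenone (−10.9 against −7.8 mmHg).

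**Conclusion.** The point holds as a defect of definition. By the wording of section 7.2 and Synopsis 2.2, control reached on rescue amlodipine is credited to the assigned drug. A difference in rescue use would move the comparison towards the arm with more rescue by c × (r1 − r0).

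The amount is unknown: 0.5 to 7.5 points over the unequal-rescue cases assumed here, and zero if rescue and post-rescue control are equal. The documents do not show that a bias will occur or which drug it would favour. The endpoint is secondary and unpowered, has no margin, and section 10.2 describes the analyses as mainly descriptive. The change is worth making because it is cheap and is best fixed before data are seen.

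**What to change.** - **Definition.** In section 7.2 and Synopsis 2.2, define control as a mean seated office reading below 140/90 mmHg at Week 12 without rescue amlodipine, with rescued patients counted as not controlled. Give the rate regardless of rescue as supportive.
- **Identification.** Take rescue to mean amlodipine given under section 5.6, so that background calcium channel blockers allowed in Synopsis 3.1 are not counted. Section 5.5.2 already records dose, indication and dates.
- **Reporting.** Tabulate rescue use by arm.
- **Primary endpoint.** Add a supportive sensitivity analysis that sets aside 24-hour systolic values measured on rescue and states how they are handled. Do not make agreement a condition for the conclusion: a second hurdle can only lower power below the planned 80%.
- **Consistency.** Reconcile sections 5.6, 5.5.1 and 4.3 item 3 on whether rescue amlodipine is permitted or is an excluded drug leading to withdrawal.

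The cost is a clause in two places, one table and one analysis; the sample size is unchanged. Control rates will be lower wherever some rescued patients reach target. The rescue decision, optional and without described blinding, becomes part of the endpoint, so both versions should be reported side by side.

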7.3 Exploratory Endpoints

The exploratory endpoints will include the followings:

- Change from baseline in urinary albumin-to-creatinine ratio (UACR);
- Change in the UACR in patients with baseline UACR more than 30 (mg/g Cr).

8 Safety Assessments

8.1 Safety Endpoints

All safety endpoints will be summarized descriptively.

The safety endpoints will include the following:

- Proportion of subjects with AEs;
- SAEs and AEs leading to discontinuation of treatment with study drug;
- Change in eGFR from baseline.

8.2 Adverse Events

An AE is defined as any untoward medical occurrence in a clinical investigation that occurs to a patient administered a pharmaceutical product, which does not necessarily have a causal relationship with this treatment.

8.2.1 Assessment of Adverse Events by the Investigator

The Investigator will assess the severity (intensity) of each AE as mild, moderate, or severe, and will also categorize each AE according to its potential relationship to study drug using the categories of **YES** or **NO**.

Mild – Asymptomatic or mild symptoms; clinical or diagnostic observations only; no intervention indicated.

Moderate – Minimal, local or noninvasive intervention indicated; limiting ageappropriate instrumental activities of daily living (eg, preparing meals, shopping for groceries or clothes, using the telephone, managing money).

Severe – Severe or medically significant but not immediately life-threatening; hospitalization or prolongation of hospitalization indicated; disabling; limiting self-care activities of daily living (ie, bathing, dressing and undressing, feeding self, using the toilet, taking medications, and not bedridden); OR life-threatening consequences; urgent intervention indicated; OR death related to an AE.

8.2.2 Causality assessment

The relationship between an AE and the administration of the study drug is to be assessed according to the following definitions:

NO (not related, unlikely to be related) – *The time course between the administration of study drug and the occurrence or worsening of the AE rules out a causal relationship and another cause (concomitant drugs, therapies, complications, etc) is suspected.*

YES (possibly, probably, or definitely related) – *The time course between the administration of study drug and the occurrence or worsening of the AE is consistent with a causal relationship and no other cause (concomitant drugs, therapies, complications, etc) can be identified.*

8.2.3 Adverse Events of Special Interest

For this study, AESIs include the following:

- Symptoms of decreased kidney function such as oliguria, swelling, and foamy urine;
- Gynecomastia, impotence, menstrual disorders, and breast-distending pain
- Side effects such as itching and dizziness;

8.3 Serious Adverse Events

An AE is considered serious if, in the view of either the Investigator, it results in any of the following outcomes:

• Death;

- A life-threatening AE;
- Requires hospitalization or prolongation of existing hospitalizations;
- A persistent or significant disability/incapacity or substantial disruption of the ability to conduct normal life functions.

8.4 Serious Adverse Event Reporting

All SAEs occurring from the time of informed consent until the end of the study must be reported to investigators within 24 hours of the knowledge of the occurrence. The Investigator must continue following the patient until the SAE has subsided or until the condition becomes chronic in nature, stabilizes (in the case of persistent impairment), or the patient dies.

8.5 Management of Potassium Levels

Potassium will be monitored closely throughout this study, with assessments of potassium concentration scheduled at all visits.

For potassium \geq 5.5 mmol/L, the patient should present to the clinical site immediately for repeat testing, and the study drug dosing need not be stopped. According to the retest results one week later, the investigator will decide whether to continue the medication.. If the potassium is normal, the original dose is given in half, and the retest is conducted one week later.

8.6 Pregnancy Reporting

If a patient becomes pregnant during the study or within the safety Follow-up Period defined in the protocol, the Investigator is to stop dosing with study drug(s) immediately and the patient should be withdrawn from the study. Early termination procedures should be implemented at that time.

9 Blood Pressure Measurement

BP will be measured at clinic visits using the following standardized procedures according to American Heart Association statement¹⁵:

- Seated office BP should be measured with the same validated arm electronic sphygmomanometer by trained clinicians or nurses at any clinical single site visit;
- Patients should not exercise, smoke, or consume caffeinated beverages or food 30 minutes prior to assessment of vital signs and BP measurement;
- Patients should be ensured that they have emptied their bladders;

- Patients should be seated for at least 5 minutes in the examination room with the back supported, feet flat on the floor, and the measurement arm supported so that the midpoint of the manometer cuff is at heart level;
- An appropriately sized cuff should be used with the bladder centered over the brachial artery;
- The arm with the higher mean BP value at Screening should be used for Screening and subsequent BP measurements;
- All BP measurements should be obtained at approximately the same time of day (7:00am- 10:00am)
- Three seated BP measurements (each measurement 1 to 2 minutes apart) should be obtained
- Using the same arm and the Omron HBP-1320 for monitoring blood pressure at each clinical site visit. Mean seated BP is defined as the average of 3 seated BP measurements at any single clinical site visit;
- If the lowest and highest SBP measurements are >15 mmHg apart, additional readings should be performed; and average the last 3 consecutive measurements (measurements 2-4). If the measurements are still >15 mmHg apart, take one additional reading and average the last 3 consecutive measurements (measurements 3-5). If the measurements are still >15 mmHg apart, take one final measurement and average the last 3 consecutive measurements (measurements 4-6).
- Place cuff of 24-h ambulatory blood pressure on bare arm with tubing passing upwards around patient's neck to be connected to the monitor on the waist to avoid the impact of frequent activities.
- The 24-h ambulatory blood pressure is assessed every 15 min during waking hours and every 30 min during sleep. ABPM data will be summarized separately as 24-hour mean, daytime mean and nighttime mean. BP readings at or after 6:00 am and before 10:00 pm are daytime readings. Readings at or after 10:00 pm and before 6:00 am the next day are nighttime readings. ABPM data require a minimum of 20 valid awake and seven valid asleep BP readings, and 70% of the reading should be valid reading, if it is not up to this standard, the ABPM needs to be re-measured. Patients should be instructed to deal with what they are expected to do during a 24-h ABP recording. Patients should keep a diary card, reporting major events occurring during the recording time, and writing down the name, dose, and time of administration of each prescribed drug, the sleeping and awakening times, time of main meals, and also a short description of any unusual activity and of any symptoms that might occur. Patient should be also instructed to follow their usual daily activities, but to remain still and to keep the arm

hanging down along the body each time the cuff starts inflation during the measurements.

• Quality control: Special attention must be placed on assessment and maintenance of the instrument's accuracy as per the manual that accompanies the instrument.

10 Statistics

